9.2.2 Study population

9.2.2.1 Eligibility criteria

Patients who meet all of the inclusion criteria and do not meet any of the exclusion criteria will be included in the study population.

Inclusion Criteria:

- 1) Patients diagnosed with at least two fibrosing ILD codes^{*1} on different dates in the patient identification period from 01-Jan-2013 to 6 months before 28-May-2020
- 2) Patients aged 18 years and older on the index date
- 3) Patients for whom data for the 12 months prior to the index date can be extracted as baseline data

*1 International Statistical Classification of Diseases and Related Health Problems (ICD-10) code or disease code: J84.1, J84.9, 8844510, 8848382, 8844341, 8848278, 8836513, 8848267, 8848302, 8839362, 8848283, 8837013, 8834158, 8848245, 8840951, 8847737

Exclusion Criteria:

- 1) Patients grouped into the underlying disease of IPF^{*1}
- 2) Patients who have met PF-ILD progression criteria during the baseline period

*1 Please refer to the ANNEX 5 for algorithm to define underlying diseases

Note: only diagnosis records without 'suspect flag' are to be considered for evaluating diagnosis related in/excl criteria"

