9.5 STUDY SIZE

The planned sample size is not based on the formal statistical hypothesis testing and statistical precision. Because the MDV database consists of >35 million patients, it is expected that the sufficient number of non-IPF fibrosing ILD patients will be included in the study.

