ANNEX 5. ALGORITHMS FOR DEFINING UNDERLYING DISEASES

The following three subgroups will be defined to assess the distribution of underlying diseases and to perform subgroup analysis by underlying diseases.

Subgroup1: Autoimmune ILD, Non-autoimmune ILD, Multiple, Unknown, IPF[#]

Subgroup2: Hypersensitive pneumonitis, Exposure-related ILD, iNSIP, Unclassifiable IIP, Sarcoidosis, RA-ILD, SSc-ILD, MCTD-ILD, Other autoimmune ILD, Other ILD, Multiple, Unknown, IPF[#]

Subgroup3: Hypersensitive pneumonitis, Exposure-related ILD, iNSIP, Unclassifiable IIP, Sarcoidosis, RA-ILD, SSc-ILD, MCTD-ILD, SLE-ILD, PM/DM-ILD, Sjogren ILD, Other autoimmune ILD, Other ILD, Multiple, Unknown, IPF[#]

#Note: Patients grouped into IPF are excluded from study population according to the exclusion criteria.

The patients will be grouped according to the following three steps.

Step 1: Patients will be grouped based on the fibrosing-ILD code on the index date

If two or more different ⁽¹⁾ disease codes specified in this step 1 exist on index date, then subgroup1=subgrou2=subgrou3=Multiple

else if disease code on index date=8844510, then Subrgou1=Autoimmune ILD, subgroup2=SSc-ILD, subgroup3=SSc-ILD

else if disease code on index date=8847737, then subgroup1=Autoimmune ILD, subgroup2=RA-ILD, subgorup3=RA-ILD

else if disease code on index date=8848382, then subrgou1=Autoimmune ILD, subgroup2=Other autoimmune ILD, subgroup3=Other autoimmune ILD

else if disease code on index date=in(8848278, 8836513, 8844341), then subgroup1=Autoimmune ILD, subgroup2=Other autoimmune ILD. Subgroup3=SLE-ILD

else if disease code on index date=in(8848267, 8848302, 8839362, 8848283, 8837013), then subgroup1=Autoimmune ILD, subgroup2=Other autoimmune ILD, subgroup3=PM/DM ILD

else if disease code on index date=8834158, then subgroup1=Autoimmune ILD, subgroup2=Other autoimmune ILD, subgroup3=Sjogren ILD

(1)Note: The disease codes in the same conditional statement are NOT considered different. For example, disease codes of 8848278 and 8836513 are in the same conditional statement and these are not considered different disease codes. On the other hand, disease codes of 8848278 and 8848267 are in the different conditional statement and these are considered different disease codes.

Step 2: Patients not grouped in the step 1 will be grouped based on the earliest underlying disease code in the lookback period and fibrosing-ILD code on the index date

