else if two or more different ⁽²⁾ earliest underlying disease codes specified in this step 2 exist AND disease code on index date=in(J84.1, J84.9), then subgroup1=subgou2=subgrou3=Multiple

else if earliest underlying disease code=in(D86.0, D86.1, D86.3, D86.8, D86.9) AND disease code on index date=in(J84.1, J84.9), then subgroup1=Non-autoimmune ILD, subgroup2=Sarcoidosis, subgroup3=Sarcoidosis

else if earliest underlying disease code=in(J67.0, J67.1, J67.2, J67.3, J67.4, J67.5, J67.6, J67.7, J67.8, J67.9) AND disease code on index date=in(J84.1, J84.9), then subgroup1=Non-autoimmune ILD, subgroup2=Hypersensitive pneumonitis, subgroup3=Hypersensitive pneumonitis

else if earliest underlying disease code=J84.0 AND disease code on index date=in(J84.1, J84.9), then subgroup1=Non-autoimmune ILD, subgroup2=Other ILD, subgroup3=Other ILD

else if earliest underlying disease code=in(J60, J61, J62.8, J63.0, J63.1, J63.2, J63.3, J63.4, J63.5, J64, J65, J66.0, J66.1, J68.0, J68.4, J70.1, J70.3, J70.4, J70.8) AND disease code on index date=in(J84.1, J84.9), then subgroup1=Non-autoimmune ILD, subgroup2=Exposure-related ILD, subgroup3=Exposure-related ILD

Note: Disease codes of 8840951 and 8848245 are added to the coitional statement.

else if earliest underlying disease code=in(M05.0, M05.1, M05.2, M05.3, M05.8, M05.9, M06.0, M06.2, M06.3, M06.4, M06.8, M06.9) AND disease code on index date=in(J84.1, J84.9, 8840951, 8848245), **then** subgroup1=Autoimmune ILD, subgroup2=RA-ILD, subgroup3=RA-ILD

else if earliest underlying disease code=in(M32.1, M32.9) AND disease code on index date=in(J84.1, J84.9, 8840951, 8848245), **then** subgroup1=Autoimmune ILD, subgroup2=Other autoimmune ILD, subgroup3=SLE-ILD

else if earliest underlying disease code=in(M33.0, M33.1, M33.2, M33.9) AND disease code on index date=in(J84.1, J84.9, 8840951, 8848245), **then** subgroup1=Autoimmune ILD, subgroup2=Other autoimmune ILD, subgroup3= PM/DM ILD

else if earliest underlying disease code=in(M34.0, M34.1, M34.8, M34.9) AND disease code on index date=in(J84.1, J84.9, 8840951, 8848245), **then** subgroup1=Autoimmune ILD, subgroup2=SSc-ILD, subgroup3=SSc-ILD

else if earliest underlying disease code=M35.0 AND disease code on index date=in(J84.1, J84.9, 8840951, 8848245), **then** subgroup1=Autoimmune ILD, subgroup2=Other autoimmune ILD, subgroup3=Sjogren ILD

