else if earliest underlying disease code=7109008 AND disease code on index date=in(J84.1, J84.9, 8840951, 8848245), **then** subgroup1=Autoimmune ILD, subgroup2=MCTD-ILD, subgroup3=MCTD-ILD

else if earliest underlying disease code=in(8841317, 8850417, 8848245, M35.2, M35.3, M35.4, M35.5, M35.6, M35.7, M35.8, M35.9, M30.0, M30.1, M30.2, M30.3, M30.8, M31.0, M31.1, M31.2, M31.3, M31.4, M31.6, M31.7, M31.8, M31.9) AND disease code on index date=in(J84.1, J84.9, 8840951, 8848245), **then** subgroup1= Autoimmune ILD, subgroup2=Other autoimmune ILD, subgroup3=Other autoimmune ILD

(2)Note: The earliest underlying disease codes in the same conditional statement are NOT considered different. For example, earliest underlying disease codes of D86.0 and D86.1 are in the same conditional statement and these are not considered different earliest underlying disease codes. On the other hand, earliest underlying disease codes of D86.0 and J67.0 are in the different conditional statement and these are considered different earliest underlying disease codes.

Step 3: Patients not grouped in the step 1 and 2 will be grouped based on the fibrosing-ILD code on the index date

else if disease code on index date=in(5163005, 5150011, 8849927) AND no other fibrosing-ILD code on the index date, **then** subgroup1=subgroup2=subgroup3=IPF. These patients will be excluded from study population.

else if two or more different ⁽³⁾ disease codes including disease code of IPF specified in this step 3 exist on index date, **then** subgroup1=subgorup2=subgrou3=Multiple

else if disease code on index date=in(8850547, 8845727), **then** subgroup1=Non-autoimmune ILD, subgroup2=iNSIP, subgroup3=iNSIP

else if disease code on index date=in(5168008, 5168009, 5150001, 8845731, 8845640, J84.9), **then** subgroup1=Non-autoimmune ILD, subgroup2=Unclassifiable IIP, subgroup3=Unclassifiable IIP

else if disease code on index date=in(1363003, 8845663, 8845714, 8845719, 5168010), **then** subgroup1=Non-autoimmune ILD, subgroup2=Other ILD, subgroup3=Other ILD

else if disease code on index date=in(8840951, 8848245), **then** subgroup1=Autoimmune ILD, subgroup2=Other autoimmune ILD, subgroup3=Other autoimmune ILD

else subgroup1=subgroup2=subgroup3=Unknown

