secondary Sjogren's syndrome	M350	8848298	J84.1, J84.8, J84.9, J99.0, J99.1	Autoimmune	Other-autoimmune/CTD ILD	Sjogren ILD

overlap syndrome	M351	8841317	J84.1, J84.8, J84.9, J99.0, J99.1	Autoimmune	Other-autoimmune/CTD ILD	Other-autoimmune/CTD ILD
anti-ARS antibody syndrome	M351	8850417	J84.1, J84.8, J84.9, J99.0, J99.1	Autoimmune	Other-autoimmune/CTD ILD	Other-autoimmune/CTD ILD
mixed connective tissue disease	M351	7109008	J84.1, J84.8, J84.9, J99.0, J99.1	Autoimmune	MCTD-ILD	MCTD-ILD
interstitial pneumonia due to collagen disease	M351	8848245	J84.1, J84.8, J84.9, J99.0, J99.1	Autoimmune	Other-autoimmune/CTD ILD	Other-autoimmune/CTD ILD
Behcet's disease	M352	1361002	J84.1, J84.8, J84.9, J99.0, J99.1	Autoimmune	Other-autoimmune/CTD ILD	Other-autoimmune/CTD ILD
vulval Behcet's disease	M352	1361011	J84.1, J84.8, J84.9, J99.0, J99.1	Autoimmune	Other-autoimmune/CTD ILD	Other-autoimmune/CTD ILD

ocular Behcet's disease	M352	8845881	J84.1, J84.8, J84.9, J99.0, J99.1	Autoimmune	Other-autoimmune/CTD ILD	Other-autoimmune/CTD ILD
vasculo-Behcet's disease	M352	1361009	J84.1, J84.8, J84.9, J99.0, J99.1	Autoimmune	Other-autoimmune/CTD ILD	Other-autoimmune/CTD ILD
oral Behcet's disease	M352	1361010	J84.1, J84.8, J84.9, J99.0, J99.1	Autoimmune	Other-autoimmune/CTD ILD	Other-autoimmune/CTD ILD
neuro-Behcet disease	M352	1361005	J84.1, J84.8, J84.9, J99.0, J99.1	Autoimmune	Other-autoimmune/CTD ILD	Other-autoimmune/CTD ILD
entero-Behcet disease	M352	8842203	J84.1, J84.8, J84.9, J99.0, J99.1	Autoimmune	Other-autoimmune/CTD ILD	Other-autoimmune/CTD ILD
incomplete Behcet disease	M352	8846052	J84.1, J84.8, J84.9, J99.0, J99.1	Autoimmune	Other-autoimmune/CTD ILD	Other-autoimmune/CTD ILD
polymyalgia rheumatica	M353	7250004	J84.1, J84.8, J84.9, J99.0, J99.1	Autoimmune	Other-autoimmune/CTD ILD	Other-autoimmune/CTD ILD

diffuse eosinophilic fasciitis	M354	8839540	J84.1, J84.8, J84.9, J99.0, J99.1	Autoimmune	Other-autoimmune/CTD ILD	Other-autoimmune/CTD ILD
eosinophilic fasciitis	M354	7294009	J84.1, J84.8, J84.9, J99.0, J99.1	Autoimmune	Other-autoimmune/CTD ILD	Other-autoimmune/CTD ILD
acrosclerosis	M355	7108005	J84.1, J84.8, J84.9, J99.0, J99.1	Autoimmune	Other-autoimmune/CTD ILD	Other-autoimmune/CTD ILD
multifocal fibrosclerosis	M355	8836987	J84.1, J84.8, J84.9, J99.0, J99.1	Autoimmune	Other-autoimmune/CTD ILD	Other-autoimmune/CTD ILD
Weber-Christian disease	M356	8830767	J84.1, J84.8, J84.9, J99.0, J99.1	Autoimmune	Other-autoimmune/CTD ILD	Other-autoimmune/CTD ILD

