hyperkinetic syndrome	M357	7285007	J84.1, J84.8, J84.9, J99.0, J99.1	Autoimmune	Other-autoimmune/CTD ILD	Other-autoimmune/CTD ILD

familial ligament relaxation	M357	8831279	J84.1, J84.8, J84.9, J99.0, J99.1	Autoimmune	Other-autoimmune/CTD ILD	Other-autoimmune/CTD ILD
eosinophilia-myalgia syndrome	M358	7101038	J84.1, J84.8, J84.9, J99.0, J99.1	Autoimmune	Other-autoimmune/CTD ILD	Other-autoimmune/CTD ILD
IgG4-related disease	M359	8848113	J84.1, J84.8, J84.9, J99.0, J99.1	Autoimmune	Other-autoimmune/CTD ILD	Other-autoimmune/CTD ILD
systemic autoimmune disease	M359	8836526	J84.1, J84.8, J84.9, J99.0, J99.1	Autoimmune	Other-autoimmune/CTD ILD	Other-autoimmune/CTD ILD
collagen disease	M359	7109004	J84.1, J84.8, J84.9, J99.0, J99.1	Autoimmune	Other-autoimmune/CTD ILD	Other-autoimmune/CTD ILD
anemia associated with collagen disease	M359	8833428	J84.1, J84.8, J84.9, J99.0, J99.1	Autoimmune	Other-autoimmune/CTD ILD	Other-autoimmune/CTD ILD
pericarditis of collagen disease	M359	4239017	J84.1, J84.8, J84.9, J99.0, J99.1	Autoimmune	Other-autoimmune/CTD ILD	Other-autoimmune/CTD ILD
polyarteritis nodosa	M300	8833125	J84.1, J84.8, J84.9, J99.0, J99.1	Autoimmune	Other-autoimmune/CTD ILD	Other-autoimmune/CTD ILD

eosinophilic granulomatosis with polyangiitis	M301	8848338	J84.1, J84.8, J84.9, J99.0, J99.1	Autoimmune	Other-autoimmune/CTD ILD	Other-autoimmune/CTD ILD
juvenile multiple arteritis	M302	8835258	J84.1, J84.8, J84.9, J99.0, J99.1	Autoimmune	Other-autoimmune/CTD ILD	Other-autoimmune/CTD ILD
acute febrile mucocutaneous lymph node syndrome	M303	4461009	J84.1, J84.8, J84.9, J99.0, J99.1	Autoimmune	Other-autoimmune/CTD ILD	Other-autoimmune/CTD ILD
Kawasaki's disease	M303	4461003	J84.1, J84.8, J84.9, J99.0, J99.1	Autoimmune	Other-autoimmune/CTD ILD	Other-autoimmune/CTD ILD
ischemic heart disease due to Kawasaki's disease	M303	8831474	J84.1, J84.8, J84.9, J99.0, J99.1	Autoimmune	Other-autoimmune/CTD ILD	Other-autoimmune/CTD ILD
Kawasaki disease-related coronary artery aneurysm	M303	4461004	J84.1, J84.8, J84.9, J99.0, J99.1	Autoimmune	Other-autoimmune/CTD ILD	Other-autoimmune/CTD ILD
incomplete Kawasaki disease	M303	8846336	J84.1, J84.8, J84.9, J99.0, J99.1	Autoimmune	Other-autoimmune/CTD ILD	Other-autoimmune/CTD ILD
polyangiitis overlap syndrome	M308	8837016	J84.1, J84.8, J84.9, J99.0, J99.1	Autoimmune	Other-autoimmune/CTD ILD	Other-autoimmune/CTD ILD

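### Annex 5 Step 2 ranks codes that name no particular connective tissue disease equally with specific ones, so some one-disease patients fall into Other autoimmune ILD or Multiple

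*Combined protocol and SAP*

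**What the plan says.** Annex 5 groups patients in three steps. Step 1 uses disease-specific ILD codes on the index date. Step 2 covers the rest: "Patients not grouped in the step 1 will be grouped based on the earliest underlying disease code in the lookback period", combined with the fibrosing-ILD code on the index date. Its rules are:

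- **Multiple.** Two or more different earliest codes, with J84.1 or J84.9 on the index date, give Multiple in Subgroups 1, 2 and 3. Note (2) says that only codes within the same conditional statement are not different.
- **Specific CTDs.** RA (M05/M06), SLE (M32), PM/DM (M33), SSc (M34), Sjogren (M35.0) and MCTD (7109008) each have their own statement.
- **Other autoimmune ILD.** The last statement begins "else if earliest underlying disease code=in(8841317, 8850417, 8848245, M35.2, M35.3" and runs on to include M35.9.
- **Index codes.** A note says: "Note: Disease codes of 8840951 and 8848245 are added to the coitional statement". The CTD statements therefore accept 8840951 and 8848245 as index codes as well as J84.1 and J84.9. The Multiple rule does not.

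The linkage table in Annex 6 lists 8848245 as "interstitial pneumonia due to collagen disease". Under M35.9 it lists collagen disease (7109004), systemic autoimmune disease (8836526), "anemia associated with collagen disease" (8833428), pericarditis of collagen disease (4239017) and IgG4-related disease (8848113). All map to the other-autoimmune group.

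Section 9.7.3 applies the three subgroupings to background characteristics, the primary outcome and the secondary outcomes.

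**The concern.** By their names, 8848245 and the four M35.9 codes other than IgG4-related disease say that a collagen or autoimmune disease is present, or that it has a complication, without saying which. Recorded beside M34 or M05, such a code need not mean a second disease. Step 2 still treats it as a rival, so the order of two entries in a 12-month window can decide whether a patient with systemic sclerosis counts as SSc-ILD.

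Section 7 makes incidence by underlying disease an aim of the study. Where the generic code wins, the specific subgroups lose patients who belong in them, and Other autoimmune ILD and Multiple gain patients with a single named disease. Section 9.9 does not mention misclassification of underlying disease, and no analysis in Section 9.7.4 is aimed at the grouping rule.

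**Working it through.** The plan states no figure on this point (Section 9.5: "The planned sample size is not based on the formal statistical hypothesis testing and statistical precision"), so there is nothing to reproduce. The check applies the Annex 5 rules to constructed code histories.

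**Inputs.** One specific CTD (M34, M05 or M33), one generic code (8848245 or an M35.9 code), one index code (J84.1, J84.9, 8848245 or 8840951), and three orders of first record in the lookback. This gives 3 × 2 × 4 × 3 = 72 patterns, or 6 for each combination of index code and order. No Step 1 code is on the index date. Earliest is read as the earliest date, and two earliest codes as a tie on that date.

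| Index code | Specific first | Same first date | Generic first |
|---|---|---|---|
| J84.1 | kept 6/6 | Multiple 6/6 | Other autoimmune 6/6 |
| J84.9 | kept 6/6 | Multiple 6/6 | Other autoimmune 6/6 |
| 8848245 only | kept 6/6 | kept 6/6 | Other autoimmune 6/6 |
| 8840951 only | kept 6/6 | kept 6/6 | Other autoimmune 6/6 |

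Patterns losing the label: 2 × (6 + 6) + 2 × 6 = 36 of 72. M32 has its own statement of the same form and behaves alike. A Step 1 code on the index date (for example 8844510) fixes the label before Step 2 is reached.

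**Which subgroupings move.** With the generic code first, Subgroup 1 stays Autoimmune. SSc and RA patients move in Subgroups 2 and 3. SLE and PM/DM patients move only in Subgroup 3, because Subgroup 2 already places them in Other autoimmune ILD. A tie with J84.1/J84.9 moves all three: the patient loses even Autoimmune, although both codes are autoimmune.

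**Limit for 8848245.** Section 9.2.2.1 includes it among the fibrosing-ILD entry codes ("8848283, 8837013, 8834158, 8848245, 8840951, 8847737"), and Section 9.1 sets the index at the second such diagnosis. Within the identification period it can therefore fall on only one date before the index. Suppose 8848245 recurs every g days, so that the index is its second date, and an established specific CTD is coded every s days. The single earlier 8848245 date is day −g. The first specific code in the lookback falls no later than day −365 + s. The generic code cannot come first if −365 + s ≤ −g, that is if g + s ≤ 365. With g = s = 90 the sum is 180, and the label is kept. What remains is mainly patients whose specific CTD is first coded on or after that single date, or is coded rarely. The M35.9 codes are not entry codes and have no such limit.

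**Possible size (assumed inputs).** Among specific-CTD patients who reach Step 2, let p be the share who also carry a generic code. Of these, let e be the share with the generic code earlier and t the share tied.

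- J84.1/J84.9 index, loss = p(e + t): 0.1 × (0.2 + 0.1) = 3%; 0.3 × (0.33 + 0.33) = 20%; 0.5 × (0.1 + 0.8) = 45%.
- Index 8848245 or 8840951 only, loss = p × e: 0.1 × 0.2 = 2%; 0.3 × 0.33 = 10%; 0.5 × 0.1 = 5%.

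These figures suit the M35.9 codes. For 8848245 the limit above makes e small in regularly coded patients.

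**The case against.** The strongest reply is that Annex 5 already contains guards. Step 1 settles patients with a disease-specific ILD code on the index date. A tie resolves to the specific disease when the only index code is 8848245 or 8840951. The entry-code role of 8848245 limits how often it can come first. The Section 9.7.4 analysis that moves the index to the first fibrosing-ILD code largely removes the problem for 8848245, which then cannot precede the index within the identification period. The Step 2 entry also has a purpose: a patient whose only CTD code is 8848245 and whose index code is J84.9 would otherwise fall to Unclassifiable IIP in Step 3. All of this stands. It narrows the point for 8848245, but does nothing for the M35.9 codes.

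Four stronger readings are tempting, and the documents do not support them:

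- *Every patient with such a code loses the specific label, because Annex 6 lists the code.* The loss is conditional, and it comes from the earliest-code and tie rules in Annex 5.
- *The loss is greatest in patients whose lung disease is explicitly linked to their collagen disease.* In the tabulation, index code 8848245 loses the label in 6 of 18 patterns, against 12 of 18 for J84.1 or for J84.9.
- *8848245 often comes first because it recurs throughout the lookback.* As an entry code it cannot do so within the identification period.
- *The code "secondary Sjogren's syndrome" should be treated in the same way.* It may be a genuine second condition, so Sjogren ILD or Multiple is defensible, and moving it would be a preference.

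**Conclusion.** The point holds in a limited form. Annex 5 Step 2 gives no precedence to a specific CTD over five codes that name none, and by its stated rules a patient with one disease can be placed in Other autoimmune ILD or Multiple. The clearer exposure is from the four M35.9 codes; that from 8848245 is narrow.

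The number of patients is not in the documents, and the 2% to 45% range rests entirely on assumed inputs. The conclusion also assumes that the code names mean what they say and that two earliest codes means a tie on one date. The effect is confined to the descriptive results by underlying disease and to the distribution of those diseases. Regrouping adds and removes no one, so the overall Kaplan-Meier estimate is unchanged. The correction is worth making before the subgroup results are read as disease-specific incidence, but it does not threaten the primary estimate.

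**What to change.** In Annex 5 Step 2, with Annex 6 aligned:

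1. Use 8848245, 7109004, 8836526, 8833428 and 4239017 as underlying-disease codes only when no specific CTD code is present in the lookback.
2. When a specific CTD code is present, ignore these five in deciding which code is earliest and whether codes are different.
3. Keep them mapped to Other autoimmune ILD when they are the patient's only CTD code.
4. Report how many patients change group, by index code and by subgroup.

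Secondary Sjogren stays as it is. No new data are needed. The cost is that M35.9 must be split at billing-code level, so that IgG4-related disease remains a specific code, and that the earliest-code and tie logic in the grouping program needs a small change and a re-check under Section 9.8.
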